3.4 Analysis

Planned analyses specific to each study aim:

1. **To identify the suitability, feasibility of delivering CMR in people with CRPS.** In order to answer the overarching research question the total number of sessions, their duration and frequency will be described as well as the presence of any exacerbation of symptoms during the intervention will be recorded rehabilitation diary, which will be handed to the lead investigator during session 2.

Furthermore, descriptive comments regarding both delivering and receiving the intervention will be collected on the interview sessions, goals, duration, frequency and modality of delivery of CMR. The diary will be analysed in order to gain insight on the adherence, efficiency, acceptability, and safety of the intervention.

2. **To determine the feasibility of running an appropriately powered efficacy study on the effectiveness of CMR in CRPS.** In order to gain some

preliminary insights into the potential effectiveness of the intervention, we will inspect for each person the change in scores on each outcome measure, relative to clinically meaningful differences. Pre- and Post-intervention clinical assessments data will be described and summarized, and their distribution will be ascertained using IBM SPSS Statistics (SPSS Inc, Chicago USA).

4. Research procedure risks and benefits

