 - b. Feasibility: to determine the degree to which the intervention can be easily and safely delivered by a trained treatment partner and received by a CRPS patient.

Design

A feasibility study design will be used to address the aims of this research.

Study population

CRPS patients who access the CRPS Service at the Royal United Hospital in Bath and their treatment partner (i.e. participants' relative or friend).

Study sample

A total sample of ten participants will be recruited for the study: five people with CRPS who access the CRPS Service at the Royal United Hospital and their treatment-partner (i.e. participants' husband, wife, friend, etc.). This sample is considered sufficient for this type of study to obtain enough data to meet the identified aims of this study.

Description of study population

Recruitment selection criteria

1) CRPS patients from the CRPS Service at the Royal United Hospital.

Inclusion criteria:

- Participants meet the Budapest criteria for Type I CRPS⁴ (i.e. the diagnostic criteria for CRPS) in one limb (unilateral).
- Pain duration for a minimum of 3 months.
- 18 years in age or older.
- Able to understand verbal and written English.
- Willing to participate and provide written informed consent.
- Have someone available to act as treatment facilitator and consent to participate in the study.

Exclusion criteria:

- Presence of any co-morbidity that may influence CRPS symptoms including stroke, diabetic peripheral neuropathy, progressive neurological disease such as multiple sclerosis, and Parkinson's disease.
- Presence of Post-Traumatic Stress Disorder or other psychological conditions hindering patients' ability to engage with the intervention.
- Serious ill health.

2) Treatment partner

Inclusion criteria:

- 18 years in age or older.
- Able to understand verbal and written English.
- Willing to participate and provide written informed consent.
- Able to commit to delivering the treatment with the patient regularly within the home environment.

Exclusion criteria:

- Serious ill health.
- Inability to deliver the treatment due to time, physical, mental or other constraints.

3. Research procedures

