3.3 Methods

The outline of study sessions is presented in figure 2:

Session 1: Pre-intervention clinical assessment and Intervention Training

Session 1 will take place in a confidential clinic room at the RUH and will comprise two parts: pre-intervention clinical assessments and intervention training for treatment partner.

- **Baseline clinical assessment (Outcome measures)**

CRPS participants will be asked to fill in patient-reported outcome measures (PROMS) as follows:

Pain (Neuropathic Pain Symptom Inventory²⁰ and Numerical Rating Scale²¹); Pain interference (Neuropathic Pain Symptom Inventory²⁰);

*Neuropathic Pain Symptom Inventory*²⁰: The Neuropathic Pain Symptom Inventory (NPSI) is one of the most widely used tools for characterizing neuropathic pain symptom severity. The NPSI is comprised of five subscales, each representing different dimensions of neuropathic pain: burning spontaneous pain (burning), pressing spontaneous pain (pressing), paroxysmal pain (paroxysmal), evoked pain (evoked), and paraesthesia/dysesthesia. Moreover, the NPSI has good construct validity, high test-retest reliability, and good sensitivity to change in people with peripherally mediated neuropathic pain.

*Numerical Rating Scale*²¹: The Numerical Rating Scale (NPRS-11) is an 11-point scale for self-report of pain. It is the most commonly used unidimensional pain scale. The respondent selects a whole number (integers 0–10) that best reflects the

intensity (or other quality if requested of his/her pain. The anchors are 0 = no pain and 10 = extreme pain/worst possible pain (there are various different wordings of the upper anchor). It is often categorised into: no pain = 0, mild pain= 1-3, moderate pain = 4-6, severe pain = 7-10. Moreover NPRS has shown to be highly correlated with the Visual Analogue Scale (VAS), ranging from 0.86 to 0.95 and has a high test-retest reliability ($r = 0.95$)²²

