movements and positions, activity simplification, pacing, planning, assistive devices, gadgets and equipment) or help. It includes numeric rating scales evaluating impact of conditions on e.g. pain, fatigue, mood and also 138 activities within 14 domains (sub-scales). This include: Eating /Drinking, In the Bathroom/ Personal Care, Getting Dressed/ Undressed, Bathing/ Showering, Cooking, Moving Around Indoors, Cleaning the House, Laundry / Clothes Care, Moving and Transfers, Communication, Moving Around Outside/ Shopping, Gardening/ Household Maintenance, Caring and Hobbies, Leisure and Social Activities. The EDAQ was originally developed and partially tested in the mid-1990's with women with rheumatoid arthritis in Sweden^{32,33} and translated into English by Beaton et al, 2000. It has been psychometrically tested several conditions including chronic pain³⁴.

PROMIS-29 v2.0 profile³⁰: The PROMIS-29 v2.0 profile measure assesses pain intensity using a single 0–10 numeric rating item and seven health domains (physical function, fatigue, pain interference, depressive symptoms, anxiety, ability to participate in social roles and activities, and sleep disturbance) using four items for each domain. PROMIS-29 has an excellent test-retest validity (≥ 0.80)²⁶

EQ-5D-5L³⁶: The descriptive system comprises five dimensions: mobility, self-care, usual activities, pain/discomfort and anxiety/depression. Each dimension has 5 levels: no problems, slight problems, moderate problems, severe problems and extreme problems. The patient is asked to indicate his/her health state by ticking the box next to the most appropriate statement in each of the five dimensions. This decision results in a 1-digit number that expresses the level selected for that dimension. The digits for the five dimensions can be combined into a 5-digit number that describes the patient's health state. The EQ VAS records the patient's self-rated health on a vertical visual analogue scale, where the endpoints are labelled 'The best health you can imagine' and 'The worst health you can imagine'. The VAS can be used as a quantitative measure of health outcome that reflect the patient's own judgement. EQ-5D-5L exhibits excellent psychometric properties across a broad range of populations, conditions and settings³⁷.

Furthermore, CRPS participants will undergo a clinical test to measure their tactile acuity, the two-point discrimination threshold (2PD³⁸), which will be assessed at the

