Intervention phase:

The CMR home-intervention involves the recommended treatment plan being delivered by the treatment partner over a four-week period. The CRPS patient and treatment partner can refer to the written guidance provided for the different recommended tasks (an example can be found in the Appendix section 1). As part of a feasibility study the CRPS-patient and treatment partner would have agreed with [name] about the duration and frequency of the intervention sessions and this will be recorded in the written treatment plan. [name] will encourage treatment partner to deliver the intervention daily. A rehabilitation diary will be provided to record frequency and duration of treatment sessions and any other comments (see Appendix 2 for an example).

Weekly Zoom meetings will be agreed between the CRPS-participant, treatment partner, [name] and [name] (Cognitive Multisensory Rehabilitation Centre, Italy) in order to evaluate progress on the intervention and modify treatment plan if required (e.g. increasing the complexity of the tasks or adding new CMR tasks). [name] who will supervise the CMR treatment during the weekly zoom calls, providing further specialist CMR knowledge.

Session 2: Post-intervention clinical assessments

Following the four-week home-delivered intervention, CRPS patients and treatment partner will be invited to undergo the post-intervention clinical assessment session at the RUH in Bath. Post-intervention clinical assessments includes a repeat data collection of the self-reported measures completed at session 1 (see section Session 1).

Furthermore, CRPS-patients and treatment partner will be invited to attend an interview by [name] in order to gain insight in their experience of delivering/receiving CMR. The interview questions will be devised in order to gain insights on adherence, efficiency, acceptability, and safety of the intervention. This interview will include the discussion of:

- Content,
- Goals,
- Duration,
- Frequency and
- Modality of delivery of CMR

The anticipated total duration of session 1 is up to 1 hour.

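### Individual changes are benchmarked only against clinically meaningful differences, with no measurement-error criterion, so changes that re-test error can produce may be read as early evidence of effectiveness

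*Protocol*

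**What the plan says.** Section 3.4, item 2 concerns the feasibility of a later powered efficacy study. To gain "preliminary insights into the potential effectiveness of the intervention", the protocol says "we will inspect for each person the change in scores on each outcome measure, relative to clinically meaningful differences". The next sentence adds a group description: "Pre- and Post-intervention clinical assessments data will be described and summarized, and their distribution will be ascertained". No numerical threshold, standard error of measurement, minimal detectable change or reliable change index appears.

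The data are few. Under Study sample: "A total sample of ten participants will be recruited for the study: five people with CRPS". The other five are treatment partners. There is one group. The questionnaires are completed at Session 1 and repeated at Session 2, after an intervention "being delivered by the treatment partner over a four-week period".

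Section 3.3 gives test-retest figures for two instruments. The pain NRS "has a high test-retest reliability", with r = 0.95. For the other, "PROMIS-29 has an excellent test-retest validity", with a figure of at least 0.80, which I read as a reliability. Section 3.4 uses neither.

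**The concern.** A clinically meaningful difference says how large a change must be to matter to a patient. It does not say how large a change one stable patient can show when measured twice. If the meaningful difference for an instrument lies inside its measurement error, passing it is weak evidence that the patient changed at all.

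Usually a control group or a repeated baseline would show how much scores move without treatment. This study has neither. The group summary describes the same five patients and cannot separate change from error.

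The Introduction says that the findings will inform larger effectiveness studies. Changes due to error could enter that reading unmarked.

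**Working it through.** The protocol states no power, SD, threshold or error rate for this comparison, so there is no figure of its own to reproduce. The check asks how often a patient with no true change would pass a threshold.

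**Inputs from the protocol**
- Reliability r = 0.95 (NRS) and at least 0.80 (PROMIS-29), section 3.3.
- Five patients, Study sample.
- Nine instruments, counted from section 3.3: NPSI, NRS, CPAQ-revised, Tampa scale, Bath body perception scale, EDAQ, PROMIS-29, EQ-5D-5L and two-point discrimination. This gives 5 x 9 = 45 patient-by-instrument comparisons.

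**Assumptions**
- Normal errors and no true change.
- Thresholds of 0.3 to 1.0 baseline SD.
- For the NRS, an SD of 2 points (range 1.5 to 2.5) and a threshold of 1 or 2 points.

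**Formulas**
- SD of change = SD x sqrt(2(1 - r)). This is 0.632 SD at r = 0.80 and 0.316 SD at r = 0.95.
- Chance of apparent improvement = 1 - Phi(threshold / SD of change).
- 95% minimal detectable change (MDC95) = 1.96 x SD x sqrt(2(1 - r)). This is 1.24 SD at r = 0.80 and 0.62 SD at r = 0.95.

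**Chance per patient per outcome, no true change**

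| Threshold | r = 0.80 | r = 0.95 |
|---|---|---|
| 0.3 SD | 31.8% | 17.1% |
| 0.5 SD | 21.5% | 5.7% |
| 0.8 SD | 10.3% | 0.6% |
| 1.0 SD | 5.7% | 0.1% |

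For example, at 0.5 SD and r = 0.80: 0.5 / 0.632 = 0.79, and 1 - Phi(0.79) = 21.5%.

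**Across the study at 0.5 SD**
- At least one of five patients passes on a given outcome: 1 - (1 - p)^5 = 70% at r = 0.80 and 25% at r = 0.95.
- If one reliability applied to all nine instruments, the expected number among 45 comparisons is 45 x 0.215 = 9.7 or 45 x 0.057 = 2.6. Expected counts do not require the outcomes to be independent.

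**Pain NRS at r = 0.95, SD 2**
- SD of change = 2 x 0.316 = 0.632 points.
- 2-point threshold: 0.1%, or 0.9% allowing for whole-number scoring (cut at 1.5). Over SDs of 1.5 to 2.5 this is below 0.1% to 0.6%, or 0.1% to 2.9% with whole-number scoring.
- 1-point threshold: 5.7%, or 21% with whole-number scoring.

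**Lower stability over four weeks**
- At an assumed r = 0.60, a 0.5 SD threshold is passed by 29%, or 13 of 45.

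**With MDC95 shown as well**
- A change beyond MDC95 in the favourable direction occurs by error in at most 2.5% of comparisons: 45 x 0.025 = 1.1, and 1 - 0.975^5 = 12% for at least one of five patients on a given outcome.
- This holds only if the SD and r used are right. If MDC95 is set from r = 0.80 but the true value is 0.60 (SD of change 0.894 SD), the rate is 1 - Phi(1.24 / 0.894) = about 8%.

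**The case against.** The plan only inspects changes, for preliminary insight. It does not classify or count responders and has no success or go/no-go rule. Comparing a change with a meaningful difference does not forbid also considering measurement error. Threshold values per instrument may be in an analysis plan that is not shown. All of this stands, and it limits the consequence to interpretation. It does not remove the point: the protocol has named its benchmark, and supplying values for that benchmark would not bring in measurement error.

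A reader might infer three stronger things that the documents do not support.

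- That many false improvements are to be expected. This depends on thresholds and SDs that the protocol does not give. At r = 0.95 with a large threshold, almost none are expected.
- That counting every subscale gives dozens of false improvements. The protocol speaks of each outcome measure and does not say that every subscale is judged. Numerical test-retest figures exist for only two instruments, and 0.80 is a floor. The Bath scale, for instance, has only Cronbach's alpha (0.66) and kappa (0.87).
- That the view of effectiveness rests on this comparison alone. The same item also summarises the group's scores before and after treatment.

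It can also be said that a strict requirement to exceed 1.24 SD is heavy for a descriptive study of five people, and that passing it would still not show an effect of CMR. Both are fair. They argue for showing MDC95 beside each change and limiting the interpretation, rather than for a hard dual threshold.

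**Conclusion.** The point holds as one of interpretation. The named benchmark for individual change has no measurement-error criterion, and the design has nothing else that separates change from re-test error.

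Its size is conditional. At a reliability near 0.80 and a threshold near half an SD, about one patient in five would pass on a given outcome with no true change. At 0.95 and the same threshold it is about one in eighteen (1 / 0.057 = 17.5). A half-SD threshold lies below MDC95 at both reliabilities. For the NRS under the stated assumptions and a 2-point threshold, the problem is negligible.

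The thresholds and SDs are assumptions, and the reliabilities may not transfer. The NRS figure comes from a source titled for osteoarthritic knee pain, so error over four weeks in CRPS could be larger. No formal decision rule is affected.

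**What to change.** In section 3.4, item 2:

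- Report each individual change, in both directions and for all outcomes, against both the clinically meaningful difference and MDC95 = 1.96 x SD x sqrt(2(1 - r)), where a published reliability exists. Say so where none exists.
- Fix the differences, SDs and reliabilities, with their sources, in one table before the first Session 2.
- Describe a change that exceeds the meaningful difference but not MDC95 as not distinguishable from measurement error.
- State that even larger changes cannot be attributed to CMR without a control.

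The cost is a few sentences and one table. Fewer changes will be described as improvement, and published reliabilities may not transfer fully to CRPS over four weeks, so MDC95 should be presented as a guide.

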4.1 Anticipated risks

The potential risk for our patient participants is a temporary exacerbation of pain/discomfort, or nausea/dizziness related to the altered perception of their affected limb. These temporary changes should all settle within 24 hours after testing or the intervention. In the unlikely event that these effects persist for more than 48 hours, the participant will be advised to consult with their GP.

Procedures for recording incidents or adverse events

In the unlikely event that the participant experiences an adverse or unanticipated effect, they will be encouraged to contact the principal investigator ([name]) by phone or email who will provide advice. All symptoms and adverse events reported will be collected by the researchers and added to the participants' files. Both adverse effects related to the study (i.e. they resulted from the intervention administration or of any of the research procedures) and unexpected (i.e. not listed in the protocol as an expected occurrence) will be emailed to the research ethics committee (REC) within three days.

4.2 Anticipated benefits

We anticipate that there might be benefits in participating in the study. These include improvements in pain, limb spatial awareness, tactile acuity, body perception disturbances and physical function. Furthermore, we hope that by evaluating the feasibility of this intervention, we can develop future non-invasive treatment alternatives that can target CRPS-related signs and symptoms.

5. Ethical and legal considerations

5.1 Ethics

Prior to the commencement of this research study an application and the study protocol will be submitted to a Research Ethics Committee (NRES) through the Integrated Research Application System (IRAS) with the South West Committee.

All patients will continue to receive their routine care as appropriate and any voluntary involvement in this study will be in addition to that care. Participants will be informed that their participation is voluntary and that they can terminate the study at any time if they wish to do so without any consequences for their routine care.

Research data security, management and storage

The study will comply with the GDPR rules and the Data Protection Act. The term research data in this protocol refers to all forms including and not restricted to video recordings, paper and digital data.

Paper consent forms signed to indicate the voluntary participation in the research study will be stored securely only at the Royal United Hospital in Bath. Personally identifiable data (such as contact details, subjects' name, NHS number or date of birth) and data collected from the study will be anonymized and allocate unique identifier and then kept within a digital data file, securely stored on a password protected and encrypted shared drive at the RUH in Bath; this shared drive can be remotely accessed from secure computers at the University of West of England and Bath by [name]. The research team may look at the participants' medical history subjects' suitability for the study.

Once the study is completed and the personally identifiable data are no longer needed the file containing personally identifiable data will be deleted according to the RUH guidelines.

If the participant stop being part of a research study at any time, the research team will keep the research data about you that they already have.

Encoded descriptive and psychometric participant data will be imported and analysed using data analysis software, e.g. SPSS. These electronic files will be stored within the encrypted study network at the RUH, which is accessible only via password protected computers, and on a password protected and encrypted shared drive at UWE and UoB; the last two can be remotely accessed from secure computers at the UoB by [name] and by [name] at UWE.

Data management plan

While only [name] will have access to personally identifiable data, all named researchers will have access to the data once anonymised and encoded. The responsibilities of the data management and its analysis are listed in the following table (see table). Please note that [name] will assist in the analysis.

Data archiving

As per NHS Research Ethics Committees, paper and digital data will be stored at Royal United Hospital and kept 5 years.

Complaints

If a participant complains about how researchers have handled your information, they will need to contact the research lead, [name]. If they do not receive a satisfactory response, they will be pointed to contact the Data Protection Officer.

Information Commissioner's Office (ICO) (www.ico.org.uk or [name]).

Data management plan

While only [name] will have access to personally identifiable data, all named researchers will have access to the data once anonymised and encoded. The responsibilities of the data management and its analysis are listed in the following table.

Table 1 Data management plan

	[name]	[name]	[name]	[name]
Obtaining study consent and storing consent forms				
Collecting and storing demographic and psychometric data				
Encoding data (allocating participant code)				
Baseline clinical assessment and treatment prescription				
Follow up CMR treatment				
Collecting data post-intervention				
Transferring data to statistic program, e.g. SPSS				
Data interpretation				
Discussion of the data for publication/dissemination				
Write manuscript for publication in peer-reviewed journal				
Agree on final manuscript draft before submission				

6. Participant expenses

All reasonable participant travel and parking costs to attend research visits to Bath will be reimbursed. Funding has been secured from Royal National Hospital for Rheumatic Diseases Donated Research Funds.

7. Publication and dissemination.

Findings from this study will be written up for publication in appropriate peer-reviewed academic journals. No patient identifiable data will be used. Furthermore, these findings will be disseminated both in written and oral forms at relevant national and international conferences.

8. Scientific and statistical review

The proposed study has been scientifically peer reviewed as part of the Royal National Hospital for Rheumatic Diseases Donated Research Funds award process.

Statistical analysis will be conducted using IBM SPSS Statistics 23 (SPSS Inc, Chicago USA) and will be supervised by [name] (University of Bath).

9. Research sites and investigators

Research data collection will be undertaken at RUH in Bath by [name] (session 1 and 2). Treatment will be determined by [name] and supervised by [name] and [name] (Cognitive Multisensory Rehabilitation Centre, Italy). Data analysis will be undertaken at RUH in Bath.

10. Research costs

Award funding from a Royal National Hospital for Rheumatic Diseases Donated Research Funds grant covers the research costs for this study.

11. Proposed time frame

Month

0-2: Ethics

2-4: Identification of potential participants and recruitment

6-10: Data collection

10-12: Data analysis and dissemination

References

1. Perfetti, C. & Wopfner-Oberleit, S. D. hemiplegische Patient: kognitiv therapeutische Übungen (Pfaum, Dayton, 1997).
2. Perfetti, C. L'exercice thérapeutique cognitif pour la rééducation du patient hémiplégique, 12 (Masson, Paris, 2001).
3. Perfetti, C. et al. Il Dolore Come Problema Riabilitativo (Piccin, Padova, 2015).
